### 9.7.8. Summary of Statistical Analyses Presented in the Interim and Final Reports

The conduct of the study involves the generation of several key reports. Interim report 1 delivers the SCRI analysis for the 2023/2024 RSV season. Interim report 2 and Interim report 3 will cover the RCA conducted during the 2024/2025 RSV season: Interim report 2 will cover an indexing period from 31 May 2023 to 10 August 2024, while Interim report 3 will extend the indexing period to 10 January 2025. The final report will include the SCRI

analysis for the 2023/2024 and the 2024/2025 RSV seasons. Additionally, this final report encompasses a pooled SCRI analysis that will combine the two consecutive seasons, and will also present any subgroup analyses, providing a comprehensive view of the safety profile of ABRYSVO. Table 2 summarizes the statistical analyses included in each interim and final report.

Table 2. Summary of Statistical Analyses in Interim and Final Reports

Milestone	Analysis Reported	
Interim report 1	2023/2024 RSV season SCRI and descriptive analysis	
Interim report 2	2024/2025 RSV season 1 st RCA report (indexing period: 31 May 2023 – 10 August 2024)	
Interim report 3	2024/2025 RSV season 2 nd RCA report (indexing period: 31 May 2023 – 10 January 2025)	
Final report to the	2023/2024 RSV season SCRI and descriptive analysis	
FDA	2024/2025 RSV season SCRI and descriptive analysis	
	Combined 2 seasons SCRI and descriptive analysis	
	Any pertinent subgroup and sensitivity analyses	

# 9.8. Quality Control

The study will be conducted according to the standard operating procedures (SOPs) of IQVIA and Pfizer.

At IQVIA, all aspects of the study from protocol development to the reporting of the results will be conducted within the framework of the IQVIA Quality Management System. A Quality Control (QC) plan for the study will be developed and executed, which will include quality control on study methodology, the SAP, programming, data management and analysis, study results, conclusions, and the study report. Furthermore:

- The study QC plan will establish ownership for the execution of the individual QC steps;
- The Principal in Charge of the study will ensure that individuals responsible for the execution of specific QC steps will have the knowledge, capability, and experience necessary to perform the assigned tasks;
- The result of the execution of the individual steps of the QC plan will be documented, and will include the required corrective actions, if any. The execution of any required corrective action will also be documented;
- The QC plan will be subjected to a final review and approval for sufficiency and completeness from the Principal in Charge of the study;
- IQVIA confidentiality agreements are signed by all employees and include data protection and strict prohibitions on reidentification attempts.

#### 9.9. Limitations of the Research Methods

This study uses a large real-world data (RWD) source of U.S. older adults, which is representative of the patient population of interest. However, use of claims databases has limitations, especially regarding potential misclassification of study variables. In this study, the primary outcome of interest, GBS, will be identified based on a validated claims-based algorithm using ICD-10 codes in inpatient Medicare data. To account for the possibility of outcome misclassification, PPV-adjusted bias analysis will be conducted to assess the robustness of results.

In addition, the CMS Medicare database has a delay, i.e., "claims lag", between when a service occurs and when the claim or encounter appears in the database. It was estimated that 91% of inpatient claims, 90% of outpatient, 96% of pharmacy claims and 87% of Carrier claims were estimated to be submitted within 2 months after service date.(14, 15) Therefore, to ensure at least 90% data completeness for this study, data are allowed to mature and complete for a minimum period of 2 months after the end of follow-up period. If there is no association between ABRYSVO and GBS, the 90% data completeness is likely to overestimate the risk of GBS by no more than 10%. The PharMetrics Plus database, which consists of fully adjudicated claims, has a lag of approximately 6 months due to claim adjudication and completion.

Another potential limitation is the generalizability of these results to all older ABRYSVO-vaccinated individuals in the U.S. for which the vaccine is indicated (i.e., individuals 60 years of age and older). The CMS Medicare database is the optimal fit-for-use database for this study and primarily consists of individuals aged 65 years of age or older. Although a small portion of individuals aged less than 65 are also enrolled in Medicare, due to pre-existing comorbid conditions, they are not representative of the underlying population, and are excluded in this analysis to minimize confounding by pre-existing comorbidities. As such, a large and representative claims database, PharMetrics Plus, was selected to provide representation of individuals aged 60-64 years old. Considering more than 90% uptake of RSV vaccines were in individuals aged 65 and older, the ability to evaluate the risk of GBS in individuals aged 60-64 is anticipated to be limited. Lastly, despite the utilization of two large real-world databases, results of this study may not be generalizable to those uninsured or with other types of health insurances.

Each of the two study designs in the protocol have their own limitations.

### 9.9.1. SCRI Analysis

- Time-varying confounding is not accounted for in this study design, although this is minimized by using a short risk and control window adjacent to each other, and a seasonality adjustment for time-varying confounding in the sensitivity analysis.
- The planned study period is only powered to detect a modest to high risk of GBS based on the sample size expected (Section 9.5). However, Pfizer has an ongoing PMR PASS (C3671031) spanning 4.5 RSV seasons (or more) to detect a 2-fold increased risk of GBS following ABRYSVO vaccination using the fully adjudicated CMS Medicare claims.

### 9.9.2. RCA

• The signal detection of the observed rate of GBS in ABRYSVO recipients in comparison to the estimated background may be subject to residual confounding, although matching on key demographic characteristics will be conducted to increase comparability. Any signals from the RCA will need to be further evaluated in the SCRI analysis.

# 9.10. Other Aspects

Not applicable.

#### 10. PROTECTION OF HUMAN PARTICIPANTS

### 10.1. Patient Information

This study involves data that exist in deidentified/anonymized structured format and contain no patient personal information.

#### 10.2. Patient Consent

As this study involves deidentified/anonymized structured data, which according to applicable legal requirements do not contain data subject to privacy laws, obtaining informed consent from patients by Pfizer is not required.

### 10.3. Institutional Review Board (IRB)/ Ethics Committee (EC)

There must be prospective approval of the study protocol, protocol amendments, and other relevant documents (e.g., informed consent forms if applicable) from the relevant IRBs/ECs. All correspondence with the IRB/EC must be retained. Copies of IRB/EC approvals must be forwarded to Pfizer.

### 10.4. Ethical Conduct of the Study

The study will be conducted in accordance with legal and regulatory requirements, as well as with scientific purpose, value, and rigor and follow generally accepted research practices described in International Ethical Guidelines for Epidemiological Studies issued by the Council for International Organizations of Medical Sciences (CIOMS).(32) The study will also be conducted in accordance with Good practices for RWD studies of treatment and/or comparative effectiveness: Recommendations from the joint ISPOR-ISPE Special Task Force on real-world evidence in health care decision-making. (32, 33)

The study will also follow additional guidelines, including guidelines for GPP issued by the International Society for Pharmacoepidemiology, the FDA Guidance for Industry and FDA Staff: Best Practices for Conducting and Reporting, Pharmacoepidemiologic Safety Studies Using Electronic Healthcare Data, and GEP guidelines issued by the IEA.(34)

# 11. MANAGEMENT AND REPORTING OF ADVERSE EVENTS/ADVERSE REACTIONS

This study involves data that exist as structured data by the time of study start.

In these data sources, individual patient data are not retrieved or validated, and it is not possible to link (i.e., identify a potential association between) a particular product and medical event for any individual. Thus, the minimum criteria for reporting an adverse event (AE) (i.e., identifiable patient, identifiable reporter, a suspect product, and event) cannot be met.

### 12. PLANS FOR DISSEMINATING AND COMMUNICATING STUDY RESULTS

In the event of any prohibition or restriction imposed (e.g., clinical hold) by an applicable competent authority in any area of the world, or if the party responsible for collecting data is aware of any new information which might influence the evaluation of the benefits and risks of a Pfizer product, Pfizer should be informed immediately. The interim and final study reports describing the study results will be disseminated to the regulators (i.e., the FDA). Data may be used in regulatory communications external to the FDA for contextualization purposes. Conference abstracts and/or manuscripts based on specific endpoints of interest may be developed for external publication purposes. The study will be registered and protocols as well as final study report will be posted in the HMA-EMA catalogues.

### ANNEX 1. LIST OF STANDALONE DOCUMENTS

None.

### **ANNEX 2. ADDITIONAL INFORMATION**

### LIST OF CODES FOR RSV VACCINES

All codes will be reviewed prior to study initiation. Below are the codes used to identify RSV vaccinations.

Vaccine Name	Codes
ABRYSVO (RSVPreF)	CPT/HCPCS: 90678 (Respiratory Syncytial Virus vaccine, preF, subunit, bivalent, for intramuscular use)
	NDC: 0069020701, 00069034401, 00069034405, 00069034410, 00069246501, 00069246510, 00069246519
Arexvy (RSVPreF3 + AS01)	CPT/HCPCS: 90679 (Respiratory Syncytial Virus vaccine, preF, recombinant, subunit, adjuvated for intramuscular use)
	NDC: 58160072303, 58160074403, 58160084811
mRESVIA	CPT/HCPCS: 90683 (Respiratory Syncytial Virus vaccine, mRNA lipid nanoparticles, for intramuscular use)
	NDC: 80777034501, 80777034589, 80777034590, 80777034596

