## 9.3.1. Exposure

The exposure of interest is ABRYSVO vaccination, defined as an individual's first administration of the ABRYSVO vaccine during the indexing period (Section 9.1.1), as identified by a CPT code, HCPCS code or NDC during the indexing period. (21)

The study spans two RSV seasons, 2023/2024 and 2024/2025, and multiple vaccinations are not anticipated as ABRYSVO is currently not approved for re-vaccination and evidence

suggests that ABRYSVO provides protection for at least two RSV seasons that overlap with the study period. To deduplicate exposure occurrences, multiple vaccine records containing the same ABRYSVO vaccine product for a unique patient ID, occurring on the same day or within three days will be deduplicated. If the multiple vaccine records are more than three days apart for a unique patient ID, it will be flagged as off-label use and reported separately. The date of the first occurrence of the ABRYSVO vaccination will be defined as the index date.

The example code lists for ABRYSVO vaccine and RSV vaccines from a manufacturer other than Pfizer is listed in LIST OF CODES FOR RSV VACCINES. The list of RSV vaccine codes in the example code lists will be reviewed and updated periodically during the entire study period.

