### 9.4. Data Sources

#### 9.4.1. CMS Medicare Administrative Database

The study will use the CMS Medicare administrative database with monthly data refreshes that include Medicare Parts A, B and D. The study will be restricted to enrollees with FFS. The Medicare claims database includes well-defined longitudinal data that captures healthcare service utilization for millions of enrollees across multiple care settings. Medicare Part A captures the inpatient setting, including critical access hospitals and skilled nursing facilities; approximately 90% of inpatient claims are submitted in 2 months after a healthcare

<sup>10 Presence of any concurrent vaccination.

encounter. (18) Medicare Part B covers doctors' services and outpatient care, including outpatient emergency department and outpatient non-emergency department, as well as professional services non-laboratory and laboratory. Medicare Part D covers the pharmacy setting. Medicare claims data undergo three stages of processing: enumeration, adjudication, and final payment. The monthly data consists of a mixture of pre-adjudicated and adjudicated claims; prior research shows that the diagnosis codes rarely change (<0.5%) after adjudication. (12, 14, 15) The use of adjudicated and pre-adjudicated claims data in this study enables near real-time assessment of a potential safety signal.

In this study, the variables will be identified within the relevant care settings. The IP setting represents hospital inpatient acute facility claims, which provide information on the care and services received by patients during the entire duration of inpatient care. These have more accurate diagnosis coding compared to professional claims, as provider facilities are reimbursed based on the types of diagnosis coded, which reflect the level of treatment required. The OP/PB setting represents all outpatient and professional services claims with non-laboratory places of service and captures the broad spectrum of outpatient care regardless of care setting or provider type. Claims with laboratory places of service are excluded as they often include "rule-out-diagnoses" that may not reflect true existing or underlying conditions present in patients.

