The demographics of the Medicare FFS population and the coding system used in CMS Medicare data are substantial topics that encompass the broad characteristics of Medicare beneficiaries and the complex system for coding healthcare services, respectively. Below is an overview of both:

The Medicare FFS program covers a diverse population of older adults and some younger beneficiaries with disabilities. The majority of Medicare beneficiaries are aged 65 years of age or older, reflecting Medicare's role as a health insurance program for older adults. The distribution between male and female beneficiaries in the Medicare FFS population tends to reflect that of the older adult population in the U.S., with a higher proportion of females, especially among the oldest age groups.

Medicare beneficiaries come from diverse socioeconomic backgrounds, but the program plays a critical role for lower-income individuals who might otherwise be unable to afford health insurance. The health status of Medicare FFS beneficiaries vary widely, from healthy individuals to those with multiple chronic conditions and serious disabilities. The program covers many individuals with high healthcare needs and expenditures. Medicare FFS beneficiaries are located across the United States, including both urban and rural areas, with distribution patterns reflecting the broader population distribution.

Medicare data utilizes several coding systems to document diagnoses, procedures, and equipment used in the care of beneficiaries. These include ICD-10-CM, used for diagnosis coding in all healthcare settings; ICD-10-PCS (Procedure Coding System), used for inpatient hospital procedure coding; CPT, used in billing process for medical procedures in medical, surgical, and diagnostic services in OP/PB services; HCPCS, also used for medical procedures, such as ambulance services and durable medical equipment; and NDC, used for a

prescription drug billing. The use of these coding systems ensures that Medicare billing is standardized, allowing for the efficient processing of claims and the collection of data for analysis and policy development.

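### One ABRYSVO NDC in Annex 2 has 10 digits where the other 13 NDCs have 11; if matched literally, doses seen only as pharmacy claims under it could be missed

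*Protocol*

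**What the plan says.** Annex 2 introduces its table with the sentence "Below are the codes used to identify RSV vaccinations". For ABRYSVO it gives CPT/HCPCS 90678 and seven product codes: "NDC: 0069020701, 00069034401, 00069034405, 00069034410, 00069246501, 00069246510, 00069246519". For Arexvy it gives "NDC: 58160072303, 58160074403, 58160084811", and for mRESVIA "NDC: 80777034501, 80777034589, 80777034590, 80777034596".

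Section 9.3.1 defines exposure as the first ABRYSVO dose, "as identified by a CPT code, HCPCS code or NDC during the indexing period". Section 9.2.1.1 makes the same identification inclusion criterion 1 for both databases.

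On care settings, Section 9.4.1 says that "Medicare Part D covers the pharmacy setting". It describes "CPT, used in billing process for medical procedures in medical, surgical, and diagnostic services in OP/PB services", and names NDC as the code for prescription drug billing.

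On upkeep, Section 9.3.1 says: "The list of RSV vaccine codes in the example code lists will be reviewed and updated periodically during the entire study period". Annex 2 also promises a review of all codes before the study starts. The amendment table in Section 5 records that the RSV vaccine code list was updated in version 2.0.

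**The concern.** The exposed population of all three analyses (RCA, SCRI and the descriptive analysis at 60-64 years) is built from this list. One of its codes differs in length from all the others, and the protocol states no step that brings NDCs to a common length. A literal comparison with a field in the 11-digit style of the other 13 codes would return nothing for it.

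The CPT code covers only part of the gap. A recipient who also has a claim with CPT 90678 is still found. A dose that reaches the data only as a pharmacy claim billed by NDC has no such second route. That recipient would leave the study population, together with any GBS case that followed.

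There is little exposure to spare. Section 9.5 starts from about 1,155,000 vaccinated people and allows 15% attrition: 1,155,000 × 0.85 = 981,750. Table 1 asks for 1,153,846 people to detect an IRR of 5.0 with a 21-day risk interval, although its note calls the equal-interval calculation conservative.

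**Working it through.** No sample size, power or alpha figure of the plan is in dispute. The check is a count of the printed codes.

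**Inputs.** The three NDC lists in Annex 2.

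| Group | Number of NDCs | Digits in each | First five digits |
|---|---|---|---|
| ABRYSVO, first code (0069020701) | 1 | 10 | 00690 |
| ABRYSVO, remaining codes | 6 | 11 | 00069 |
| Arexvy | 3 | 11 | 58160 |
| mRESVIA | 4 | 11 | 80777 |

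**Count.** 1 + 6 + 3 + 4 = 14 codes; 6 + 3 + 4 = 13 have 11 digits and one has 10.

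**Likely cause.** Adding one zero in front of 0069020701 gives 00069020701. That has 11 digits and begins 00069, like the other six ABRYSVO codes. All 14 codes would then share one length. That the missing digit is a leading zero is an inference from the other six codes; the protocol does not say so.

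**Match test.** The 11-digit form 00069020701 appears nowhere in the printed list, so no other entry stands in for it. An exact text comparison of that form with the list fails. A comparison after zero-padding, or as numbers, succeeds.

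**Size.** Let N be the number vaccinated, f the share of doses seen only as pharmacy NDC claims, and s the share of those billed under this code. Under literal matching:

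lost exposures = N × f × s

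The protocol gives N (about 1 million per season) but neither f nor s. With padding or numeric matching the loss is zero. Beyond that no figure can be derived.

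**Direction of effect.** A missed recipient leaves both the cases and the denominator.
- SCRI: the comparison is within person (Section 9.7.4). Omitting people by billing code does not move the IRR unless the code is related to the day of GBS onset, and nothing in the protocol suggests that.
- RCA: observed events and expected events (background rate times person-time) fall together.
- Descriptive analysis: numerator and denominator fall together.

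What remains is a possible loss of completeness and power.

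**The case against.** The strongest reply is that a short string on paper is not a lost dose. The protocol fixes no matching rule, code formatting is commonly settled in the programming specification, and Section 9.8 commits to quality control of programming and data management. Section 9.3.1 calls these example lists and promises periodic review throughout the study. Zero-padding would recover the code without anyone noticing the misprint. This stands: the loss is conditional on literal matching and must not be stated as fact.

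The reply does not remove the point. Annex 2 presents the list as the codes in use. Data collection was planned to start on 19 August 2024; the list was revised in version 2.0 of 23 April 2025 and still carries the short code. Even if the 10-digit string is another way of writing the same product code, the list mixes two formats and states no conversion.

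A digit lost when the PDF was read cannot be excluded. The other 13 codes are intact, so this is not the likeliest explanation, but the original page should be checked.

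Two stronger readings are tempting, and the documents support neither.

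- A reader might infer that index dates shift, because a later record of the same dose would be taken as the first. That needs one dose to leave records on different dates, which the protocol nowhere says. Section 9.3.1 treats same-product records within three days as duplicates, and flags those further apart as off-label use.
- A reader might assume a percentage for the code and turn it into lost GBS cases. Any such percentage would be invented. Applying a share of pharmacy-only doses to all doses would also ignore the unknown factor f above.

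**Conclusion.** The code is wrong or inconsistent as printed, in a list on which the study relies. Severity is minor. The count is exact: 1 of 14 NDCs has 10 digits. The consequence rests on two assumptions: that the claims field holds NDCs in the 11-digit style of the other 13 codes, and that the printed string is matched to it literally. If both hold, recipients whose only record is a pharmacy claim under this code could be missed in both databases, with a loss of exposures and GBS cases that cannot be quantified from the documents. No bias in the SCRI IRR is evident, and none is claimed here.

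**What to change.** 1. Verify the first ABRYSVO NDC against the product labelling and print it in the same 11-digit format as the others, apparently 00069020701.
2. State in the code list or programming specification that all NDCs, in the list and in both databases, are normalised to 11 digits before matching.
3. Check which string the completed extractions used; Section 6 marks Interim reports 1 and 2 as completed. Re-run exposure identification only if the 10-digit string was matched literally.

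The cost is one character in Annex 2, one sentence on normalisation and one programming check. A re-run is needed only if that check shows literal matching.
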